**None**

11. If your research involves collecting a **combination** of demographic data (e.g., a combination of gender, age, race, and ethnicity) that may make a participant identifiable, you must inform the participants the following: *"For this research project, the researchers are requesting demographic information. Due to the make-up of Idaho's population, the combined answers to these questions may make an individual person identifiable. The researchers will make every effort to protect your confidentiality. However, if you are uncomfortable answering any of these questions, you may leave them blank."*

If applicable, indicate where and how participants will be informed of this.

**This information will be included in the informed consent and assent.**

## SECTION H: Data Collection

1. Attach copies of all data collection tools and methods to be used. Check all that apply.

 Questionnaire/Survey (attach questions)	 Videotaping
 Observation	 Photographing
 Interviews (attach questions and scripts)	 Audiotaping
 Focus Groups (attach questions and scripts)	 Using direct quotes
 Reviewing Medical/Education Records	 Deception
 Other:	

2. Indicate all biomedical procedures that apply to your research:

 Physical Activity	 Body Mass Index
 Venipuncture	 X-rays
 Magnetic resonance imaging (MRI)	 Anthropomorphic evaluations
 Electrocardiograms (EKGs)	 Intravenous catheter insertion
 Collection of blood samples by finger stick, heel stick, ear stick or venipuncture	
 Other:	

3. If applicable, describe the procedures being performed already for diagnostic or treatment purpose.

**N/A**

4. What are you going to ask participants to do? Provide a step-by-step description of each procedure, including the frequency and duration of each procedure. **This question is mandatory and may not be skipped.**

**Applications missing this section will not be accepted.**

All student participants will be asked to complete an online survey during class time. This will take no longer than 20 minutes. Participants in the classrooms randomly assigned to the intervention group will be asked to complete an online intervention program which will occur during class time. The program involves a comprehensive assessment of the participant's drinking and drinking-related behaviors, followed by systematic personalized feedback to the participant about their alcohol use feedback in relation to their peer group. The program will take about 30 minutes to complete. Participants will then be asked to complete a brief exit survey regarding the intervention. Participants will be asked to complete the survey at 6 weeks and 6 months in the computer lab at their school. This survey will be completed online during class periods and will take no longer than 20 minutes to complete. Participants will also complete a very brief survey to assess help seeking. This will occur at the 6 week and 6 month follow-up assessments.

5. Where will the data collection and data analysis procedures take place? (i.e., explain where you are distributing surveys, conducting interviews, etc.)

**Onsite at Capital High School and Boise High School in the computer lab via electronic methods.**

6. Does your study include plans to conduct research at an external site? (i.e., off Boise State campus. For example, an elementary school, hospital, prison, etc.)

YES  NO

If YES, indicate the external site(s) and you must attach an acknowledgement (letter or email) indicating you have permission to use their facility and personnel.

**Capital High School, Boise, ID and Boise High School, Boise, ID**

If YES, does your study include plans to conduct research at external sites that are engaged in the research? If so, will that site's IRB approve this research or will it rely upon the BSU IRB?

The external site is not engaged in the research other than in facilitating the process and sending parental informed consent letters. Additionally, a school counselor may help facilitate data collection in the computer lab with the research team. We do, however, have approval from the Boise School District Research Board to conduct the study.

7. Will monetary or other compensations be offered to the participants (e.g., gift certificates, raffle, cash payment or class extra credit?)

YES  NO

If YES, identify the amount of compensation and method of payment. Explain how participants would earn compensation if their participation is anonymous. If students are offered extra credit, you must provide other options to fulfill the research component if they do not wish to participate.

**Classroom incentives will be given to classrooms with at least a 60% response rate. These will include a \$100 gift certificate to the teacher for classroom supplies and a pizza party for the class.**

## SECTION I: PARTICIPANT PRIVACY

**Privacy** refers to persons during data collection. It is the control over the extent, timing, and circumstances of sharing oneself (physically, behaviorally, or intellectually) with others (e.g., surveys are completed in the privacy of their own home; interviews will be done in a location of their choosing where it is unlikely they will be overheard).

1. Describe the provisions to protect the privacy of the participants during the data collection procedures.

**Participants will complete all questionnaires and the intervention on a computer situated so no other person can see the computer screen. The participants will be given a code number to use during each assessment. The research staff will have a master list that links the code number to the participant. Once the 6 month follow-up data is collected the master list will be destroyed.**

## SECTION J: CONFIDENTIALITY OF DATA

**CONFIDENTIALITY:** Confidentiality refers to how DATA is handled after collection. It is the treatment of information already revealed and states that there is an expectation that it will not be divulged to others in ways that are inconsistent with the understanding of the original disclosure without permission (e.g., data is secured on a password-protected computer or locked file cabinet, data is de-identified or coded, only the researchers have access to the data).

1. Provide details as to how you plan to protect the data while on site and during travel (e.g. from data collection site back to the office). When traveling (especially overseas) or just with portable devices, data security is vital, especially if the device or data is lost or stolen. Address the storage and security of electronic data as well as any physical data, such as paper consent forms or surveys, during travel.

**All data will be collected via online surveys - it will not be transported as it is electronic.**

2. Describe how you will maintain confidentiality of the data after it has been collected, including measures to protect the identity of the participants and their responses (coding procedures, encryption, etc.).

**Confidentiality of data will be maintained through the use of a code number. All data collected through electronic means will be delivered directly to the research database upon completion of the survey. The master list of volunteer names and their corresponding code numbers will be confidential and will only be accessible by the principal investigator at BSU. After completion of the post-intervention surveys, the master list will be destroyed.**

3. Where will you store the data? A copy of the data must be kept within the campus departmental area, not stored at home. OIT offers virtual servers and storage for BSU researchers, [click](#) for more details. Describe procedures for both electronic and hard copy data.

**Survey data are collected online and will be kept on a password protected computer in a locked office. The data will be stored on a password protected computer in a locked office at Boise State and will be kept for a minimum of three years.**

4. Who will have access to the data?

**Only members of the research team will have access to the data through permission from the PI.**

5. In what format will the data be stored (e.g., paper or electronic copy)?

**The data will be stored in electronic format.**

## SECTION K: Risks and Benefits

1. What are the risks and inconveniences to the participants? Describe all known anticipated psychological, physical, sociological, financial, economic risk to participants:

Examples include, but are not limited to:

- Loss of confidentiality
- Identifiable links to individual participants
- Feeling guilty for lying in study requiring deception
- Emotional stress or discomfort (*describe below*)

**No physical, psychological, legal or economic risks or consequences to the participants are anticipated. Any potential psychological risks posed by the research are primarily related to the sensitivity of some of the measures. Items include thoughts, feelings, and personal difficulties that may be private and personal behavior such as alcohol and other drug use. These questions may make participants uncomfortable, or be perceived as an intrusion on their privacy. Participants are also asked to report on potentially illegal behaviors, such as drinking under the legal drinking age or driving after drinking. However, there is no risk of coercion of individuals, as individuals are free to delete the invitation email should they choose to do so and may discontinue involvement in the study at any time.**

- Physical injury or discomfort (*describe below*)

- Other:

2. How will you minimize these risks and their impact to the participants?

**The primary procedure for guarding against this risk is to fully inform them of their right to refuse to participate in any portion of the study or to discontinue the study altogether. [name] is a Licensed Clinical Professional Counselor and will be with the students during all assessments and the online intervention will also be prepared to respond in an appropriate and caring manner to any queries by a participant. Participants will also be provided information about follow-up counseling services.**

3. Describe how you are able to identify and handle the risks above. Provide a brief description of all relevant training, experience, education, and credentials.

**The intervention will be administered by [name] who is a Licensed Clinical Professional Counselor and is fully trained and licensed to work with students experiencing distress and provide appropriate resources for participants. In addition, this project is similar to several projects conducted by this PI and [name] with no adverse events. The PI and Co-I have extensive experience working with this population.**

**In addition, program staff are licensed mental health professionals and are trained to manage any crisis that might occur. [name] is a licensed psychologist with over 10 years experience in clinical work. [name] is a Licensed Clinical Professional Counselor with 15 years experience in clinical work.**

4. Describe your plan for an emergency situation. Even if you feel this situation is unlikely, please have a plan in case of emergency (e.g., the researcher will carry a cell phone, etc.).

**If a participant were so distressed as to represent a harm to themselves, the participant would be walked to school counselor's office where arrangements would be made to have the police escort the participant to an appropriate facility for an evaluation. [name] is a Licensed Clinical Professional Counselor - she will be administering the survey and intervention and is trained to evaluate and manage crisis situations. The PI will be available by cellular phone to supervise and manage any crisis that might occur.**

5. What are the potential direct benefits to the research participants? (This may not be applicable to your research.)

**Participants in the study who are using alcohol may decrease their drinking. Interventions such as those used in this study have been shown in the literature to decrease high-risk drinking and alcohol initiation. Thus, participating in this study has the potential to positively impact students, including those who are at high-risk for alcohol-related consequences.**

6. What are the potential broader benefits of the study?

**In addition to benefits for participants, the development and implementation of intervention programs for high school students has the potential for reducing the serious public health problem of underage drinking and the negative associated consequences. Given the relatively high rates of heavy drinking in high school, the relationship between high school drinking and drinking in college students and non-college attending young**

adults, and the relationship between underage drinking and the development of alcohol use disorders, dissemination of efficacious intervention programs has the potential for significant societal benefits. Given the potential benefit to both individual participants and society, the risks of participation are outweighed.

#### SECTION L: Unanticipated Problems/Adverse Events

**Unanticipated Problem:** includes any information that is unexpected, related or possibly related to the research, or indicates that participants or other individuals may be placed at greater risk of harm than initially anticipated by the IRB.

**Adverse Event:** Any untoward or unfavorable medical occurrence in a human participant, including any abnormal sign (for example, abnormal physical exam or laboratory finding), symptom, or disease, temporally associated with the subject's participation in the research, whether or not considered related to the subject's participation in the research.

**If an unanticipated problem or adverse event should occur, you must immediately complete and submit the IRB Incident Report Form to [[contact]](mailto:[contact]), and contact the Office of Research Compliance at [contact].**

### *Statistical Analysis Plan*

To identify reductions in alcohol use and negative alcohol-related consequences among high school seniors over the duration of the study, we will evaluate each outcome using analysis of variance in a linear or generalized linear mixed model framework, with random effects of repeated observations on students, students nested in classes, periods or teachers, and within school. We will address the appropriateness of the model for non-normal outcomes and apply the appropriate distribution as necessary, and we will assess models for the necessity of all random effects using  $AIC_C$ . The fixed effects will include treatment (intervention, control), time (baseline, 6-weeks, and 6-months), and their interaction.

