The proposed study extends the literature by examining the eCHECKUP TO GO with high school seniors over a longer follow-up period, as well as examining mediators and moderators of intervention effects. All 12th grade students at the two participating school sites will be given the opportunity to participate in the study. All participants will complete an assessment packet containing questionnaires including demographic

information, the quantity and frequency of their drinking, beliefs about both the quantity and frequency of their peers' drinking, alcohol beliefs and expectancies, problems associated with drinking, personality characteristics, and future goals (see attachment 1). Classrooms within the high school schools will be randomly assigned to the following groups: eCHECKUP TO GO and control group.

What is your research question? State your hypothesis.

**The project is designed to evaluate the following hypothesis:** Participants in the eCHECKUP TO GO intervention condition will report a reduction in their quantity of alcohol consumption and alcohol-related consequences relative to those in the control group. We are also interested in mechanisms of change (e.g. changes in estimates of peer drinking and/or drinking expectancies) and if this program is more effective for some students than others (e.g. gender, baseline drinking status, social-emotional maturity, college-bound status).

What will you do with the results of your study (e.g. contributing to generalizable knowledge, publishing, sharing at conference, etc.)? If this project is only for internal evaluation or to complete a class assignment, IRB may not be required. Please contact the ORC for additional information.

**Results of this study will be presented at conferences via oral or poster presentations and through publication in peer-reviewed journals. In addition a project summary report will be sent to the participating schools and/or school district.**

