**We anticipate the student participants will be healthy.**

2. Will your research involve vulnerable populations, such as children or adolescents under the age of 18, pregnant women, prisoners or cognitively, economically, or educationally impaired participants?

NO  YES (indicate population): \_\_\_\_\_

If yes, describe additional safeguards planned to protect the rights and welfare of this population(s):

Student participants recruited to this research study will be approximately 1000 high school seniors (ages 16-18) from Capital High School and Boise High School in the Boise School District. Classrooms within the schools will be randomized to intervention or assessment-only control conditions. Participants will be recruited from classes. A letter will be sent by the schools to parents and their students prior to the study explaining the research. Parents will be asked to return consent forms using a self-addressed stamped postcard. Students will be invited to participate in the research study during class. Those students who decline participation will participate in an alternate academic activity under the supervision of the teacher. Consent procedures will be the same for minors and 18 year old students as the Boise School District requires parental consent for 18 year old students.

The surveys will ask student participants about their own alcohol use/non-use and any negative consequences, attitudes and beliefs about alcohol use, reasons for using alcohol use, norms for alcohol use, personality characteristics, future plans, and demographic information. Similar procedures have been used in previous research with 9th grade students and high school seniors without adverse incident. Psychological risks posed by the research are primarily related to the content of the assessment measures. Items include thoughts and feelings that may be private and personal behavior such as alcohol use. These questions may make participants uncomfortable, or be perceived as an intrusion on their privacy. Although it is important to consider these potential risks, and it is important to point out the potential for these risks, we have not observed any indications of these risks materializing in all of our previous research using procedures similar to those we will use in the proposed study.

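### Classrooms are randomised, but the treatment-by-time test has no classroom-by-time random effect, and AICc may remove the classroom effect itself

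*Combined protocol and SAP*

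**What the plan says.** Section E (Purpose) sets the design: "Classrooms within the high school schools will be randomly assigned to the following groups: eCHECKUP TO GO and control group". Section F (Participant Population) repeats it: "Classrooms within the schools will be randomized to intervention or assessment-only control conditions". The hypothesis in Section E is that intervention participants "will report a reduction in their quantity of alcohol consumption and alcohol-related consequences relative to those in the control group".

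The Statistical Analysis Plan is one paragraph. It proposes linear or generalized linear mixed models "with random effects of repeated observations on students, students nested in classes, periods or teachers, and within school". It then says "we will assess models for the necessity of all random effects using" AICc. On the fixed part: "The fixed effects will include treatment (intervention, control), time (baseline, 6-weeks, and 6-months), and their interaction".

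The documents give no number or size of classrooms, no ICC, no within-student correlation, no attrition rate and no degrees-of-freedom method. The only sample figure is 450 expected participants from 1000 seniors (Section F).

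**The concern.** A reduction relative to control is a difference in change, so treatment-by-time is the test that matches the hypothesis. Because classrooms are randomised, its error term should reflect how much change varies between classrooms. The listed random effects are nesting levels only: student, class (or period, or teacher) and school. A reader may take nesting in classes as having dealt with clustering. It does so for comparisons of level between arms, but not for comparisons of change.

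Two further points carry less weight.

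- The AICc check covers all random effects, so a stated rule can remove the randomised unit from the model. This affects between-class contrasts such as the treatment main effect.
- Listing classes, periods or teachers as alternatives does not fix classroom as the cluster level. This needs clarifying, and its effect could go either way.

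At stake are an inflated false-positive rate and intervals that are too narrow for the main comparison.

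**Working it through.** **Plan's own figure.** 1000 × 0.45 = 450, as stated. The claim that 450 gives adequate power cannot be checked, because no inputs are given.

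**Why the class intercept does not help.** Take balanced complete data with m participants per class. Let σ²_ct be the class-by-time variance, σ²_e the residual variance, and σ²_w = σ²_ct + σ²_e. In a class's mean change between two times, the class and student intercepts cancel.

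- True variance of that change: 2(σ²_ct + σ²_e/m).
- Variance the model assumes without a class-by-time term: about 2σ²_w/m.
- Ratio: DE = 1 + (m − 1)ρ, with ρ = σ²_ct/σ²_w.

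As a check, six simulated datasets (30 classes of 15; SDs 0.22 for class-by-time and 0.7 for residual, a deliberately large share) were fitted by REML. The standard error of treatment × 6 months was the same with and without a class intercept in every dataset (for example 0.095 and 0.095). With class-by-time added it was 0.127–0.162. The true value is √[(2 × 0.22² + 2 × 0.49/15) × 4/30] = 0.147.

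**Assumed inputs.** About 450 participants in 36 × 12, 45 × 10 or 60 × 8 (classes × participants), which is about 28, 22 or 17 of the 1000 seniors per class. Class-by-time variance is 0.01 or 0.02 of the total. Within-student correlation is 0.5 or 0.7, so ρ runs from 0.01/0.5 = 2% to 0.02/0.3 = 6.7%.

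**Type I error, linear model, term omitted.** For a 2-df test the error is roughly 0.05^(1/DE).

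- 60 × 8, ρ = 2%: DE = 1 + 7 × 0.02 = 1.14, and 0.05^(1/1.14) = 7.2%.
- 36 × 12, ρ = 6.7%: DE = 1 + 11 × 0.0667 = 1.73, and 0.05^(1/1.73) = 17.7%.

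Simulation of the 2-df test (400,000 runs per setting, no true effect) agrees:

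| Layout | 0.01, corr 0.5 | 0.02, corr 0.5 | 0.01, corr 0.7 | 0.02, corr 0.7 |
|---|---|---|---|---|
| 36 × 12 | 8.6% | 12.5% | 11.2% | 17.8% |
| 45 × 10 | 7.9% | 11.1% | 10.0% | 15.5% |
| 60 × 8 | 7.3% | 9.7% | 8.9% | 12.9% |

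- Term always kept, with class-level df: 5.0%.
- Term entered but left to AICc: 5.0–6.7%.
- Term omitted, variance 0.0025–0.005 of total: 5.5–7.9%. At zero: 5.0%.
- Fewer, larger classes are worse. At ρ = 2%, 18 × 25 gives 13.3% with the term omitted.

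**Unequal class sizes and attrition** (assumed 15% at 6 weeks and 30% at 6 months, missing at random; REML; Monte Carlo SE 0.4–0.9 points). For variance 0.01 at correlation 0.5 and 0.02 at correlation 0.7, omitting the term gives 8.9% and 16.8% (36 × 12), or 7.4% and 13.1% (60 × 8). Keeping it gives 4.2–5.7%.

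**Generalized models, term omitted.** These were student-intercept models with the class intercept variance set to zero.

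- Binary outcome (30% prevalence, latent share 0.01–0.02): 6.9–9.5% (36 × 12) and 5.5–7.9% (60 × 8). The zero-variance error was 4.5–5.6%.
- Overdispersed count (mean 2, class-by-time SD 0.13 and 0.18 on the log scale, 36 × 12): 7.3% and 9.6%. The zero-variance error was 5.4%.
- A classroom-level analysis of change on the same data: 4.4–5.5% (binary) and 4.8–5.1% (count).

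**AICc and the class intercept** (treatment main effect, same layouts).

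| Class ICC | Class dropped | Overall error |
|---|---|---|
| 0.02 | 71–80% | 5.7–6.4% |
| 0.05 | 31–43% | 5.8–6.5% |
| 0.10 | 4–6% | 5.2–5.3% |

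With 18 classes of 25, the overall error reaches 8.1% at ICC 0.02.

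**The case against.** The strongest reply is that the harm rests on a variance that nobody has given. The feedback is individual and online, in a computer lab, with one counsellor administering survey and intervention (Sections H and K). All of that points to little class-specific change. The classroom incentive in Section H rewards response rate, not drinking. On the other side, intervention students "complete an online intervention program which will occur during class time", and Section E names perceived peer drinking as a possible mechanism, although the peer group is not said to be the classroom. This objection stands as far as size is concerned: the inflation could be zero. It does not justify a plan whose validity needs it to be zero, when a 2% share of within-student variance is enough to matter.

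A second reply is that a short plan merely leaves the term unspecified. But it does list its random effects and gives a rule for pruning them. Followed as written, the key test has no class-level error term.

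Third, naming the term and leaving it to AICc would remove most of the inflation (5.0–6.7% in these layouts). That is true here. With 18 classes of 25 at ρ = 2%, however, AICc dropped the term in 58% of trials and the error was 8.6%.

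Fourth, the generalized-model evidence is weaker. The class intercept was not included, the lowest binary result (5.5%) is within the zero-variance range, and a generalized model with class-by-time kept was not fitted. Those figures are indicative only. Attrition that depends on class or outcome was not simulated either.

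**Conclusion.** The concern holds and should be fixed. The textual omission is certain. The cancellation of the class intercept is exact for balanced linear models, and the simulations with unequal classes and attrition show similar inflation.

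For a linear outcome with class-by-time variance at 1–2% of the total, treatment-by-time runs at 7.3–17.8% instead of 5%, and a correct interval is √1.14 to √1.74, or 1.07 to 1.32 times, as wide. (The simulated upper DE is 1.74, not 1.73, because the pooled residual in the omitted model is slightly below σ²_w.) With smaller variance the inflation is slight, and with none it disappears. All of this depends on assumed class counts, variances and correlations.

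The AICc rule is a real but secondary defect. The plan does recognise clustering; it is incomplete for the contrast that tests its hypothesis.

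**What to change.** Replace the AICc clause with wording such as:

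> Classroom, the unit of randomisation, is the cluster level. Classroom and classroom-by-time random effects are retained whatever the AICc. Linear models use Kenward-Roger or Satterthwaite degrees of freedom (class-level if the variance is estimated at zero). Generalized models use class-level (between-within) degrees of freedom; if they do not converge, a classroom-level analysis of change is used. Period and teacher may be added to classroom but do not replace it. AICc is used only for non-design random effects.

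The work is a change of SAP wording and little extra analysis. The statistical cost depends on the truth.

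- **Class-by-time variance zero:** treatment-by-time intervals widen by 1–2% through degrees of freedom alone. An effect with 80% power keeps 78–79%. The test is slightly conservative (3.7–4.1%) when a zero variance estimate is paired with class-level df.
- **Variance 0.01–0.02 of total:** intervals are 8–34% wider, including the loss of degrees of freedom. An effect with 80% power under zero variance has 53–73%. That is not small, but it is the design's actual precision, which the present model would overstate.

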## SECTION F: Participant Population

1. Provide a description of the participant population you intend to recruit and collect data from. Describe the characteristics of the participant population such as gender, age ranges, ethnic background and health status, as applicable to the research.

**Participants (12th grade students; N = 1000) will be recruited from Capital High School and Boise High School in the Boise School District. All 12th grade students will be given the opportunity to participate in the study.**

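### School is a random effect open to removal by AICc, but with only two schools it should be a fixed term that is always kept; the consequence is modest.

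*Combined protocol and SAP*

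**What the plan says.** - **Model.** The Statistical Analysis Plan specifies linear or generalised linear mixed models "with random effects of repeated observations on students, students nested in classes, periods or teachers, and within school". The fixed effects are treatment, time (baseline, 6 weeks, 6 months) and their interaction. School is not among them.
- **Screening.** The same paragraph states that "we will assess models for the necessity of all random effects", with AICc as the criterion. Neither school nor class is exempted.
- **Schools.** Section F, item 1 says participants "will be recruited from Capital High School and Boise High School in the Boise School District". Section E also refers to two sites.
- **Randomisation.** Section E: "Classrooms within the high school schools will be randomly assigned to the following groups: eCHECKUP TO GO and control group". Section F, item 2: "Classrooms within the schools will be randomized to intervention or assessment-only control conditions". Neither section says that the allocation is balanced or stratified by school.

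**The concern.** The two schools are the named study sites, not a sample from a population of schools, and the randomised classrooms sit inside them. A random effect asks the data for a between-school variance, and two schools give 1 df for it. AICc then decides from that estimate whether school is modelled at all. Because school is not a fixed effect either, nothing represents it once it is dropped.

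Three things are at stake:
- a data-driven choice, made separately for each outcome, that carries almost no information;
- a school difference left in the class-level variance, which widens the interval for an arm comparison at a single time point;
- a shift in that comparison whenever the realised allocation is uneven across schools.

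**Working it through.** **Inputs from the documents.** 2 schools; classrooms randomised within schools; 1000 students × 45% response = 450 participants, which reproduces the stated figure. The number of classes, ICC, size of the school difference, alpha and power are not given. Every value for these below is an assumption.

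**1. Precision of a variance on 1 df.** The 95% interval for the between-school mean square is the observed value divided by the chi-square (1 df) 97.5% and 2.5% quantiles. It runs from 0.20 to 1,018 times the observed value. The ratio is 1018.26 / 0.19905 ≈ 5,116.

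**2. How often school drops out.** Balanced nested REML fits were simulated at one time point, with 450 students, 12, 20 or 40 classes, class ICC 0.02 or 0.05, and true school variance 0.5% to 5% of the total. Two schools drawn with variance s differ by √(2s) SD (root mean square), so these settings correspond to about 0.10 to 0.32 SD.
- The estimate is exactly zero in 24% to 58% of trials.
- AICc drops school in 50% to 92% of trials.

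With the difference held fixed instead (ICC 0.03), two separate simulations of 40 classes dropped school in 61-64% of trials at 0.2 SD and 27-31% at 0.3 SD. With 20 classes the figures were 69% and 40%.

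**3. SE of a single-time-point comparison with school omitted.** Let K be the number of classes, n = 450/K, class-mean variance v = ICC + (1 − ICC)/n, and D the school difference, with arms balanced by school. The SE ratio is √(1 + [K/(K−2)] × (D²/4)/v). With ICC 0.03:

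| K | v | D = 0.2 | D = 0.3 |
|---|---|---|---|
| 40 | 0.03 + 0.97/11.25 = 0.1162 | 1.04 | 1.10 |
| 20 | 0.03 + 0.97/22.5 = 0.0731 | 1.07 | 1.16 |

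The wider grid in step 2 gives 1% to 29%. The top of that range needs 12 classes and a school variance of 5%.

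**4. Shift under an uneven split.** With 12 of 20 intervention classes and 8 of 20 control classes in the same school, the arms differ in school mix by 0.6 − 0.4 = 0.2. The shift is 0.2 × D: 0.04 SD for D = 0.2 and 0.08 SD for D = 0.4. If equal arms were allocated without regard to school, an imbalance at least this large would occur in 1 − C(10,5)²/C(20,10) = 66% of 20-class trials and in 34% of 40-class trials.

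**5. Treatment-by-time.** Take a three-wave linear model with 20 classes of 22 (220 students per arm) and within-student correlation 0.5. The variance of a student's change is 2 × 0.5 = 1, so the SE of the baseline-to-6-month contrast is √(1/220 + 1/220) = 0.0953. A generalised least squares check (class ICC 0.03) gave 0.0953 with school omitted and with school as a constant fixed effect. With 30% dropout at 6 months it was 0.108 in both. Under a 6/4 against 4/6 split the two estimates agreed to within 0.0001.

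If the school difference changes by 0.2 SD over follow-up, 0.2 × 0.2 = 0.04 SD enters the estimate. Fitting school-by-time removes it, at an SE of 0.0953 / √(1 − 0.2²) = 0.0973, about 2% larger.

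**6. Type I error at nominal 0.05** (class-mean test, one time point).
- Allocation balanced within school: 0.047-0.052 with school fixed, 0.032-0.048 with school omitted (conservative).
- Allocation not balanced by school: 0.044-0.054 with school omitted.

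**The case against.** The strongest reply is that the SE inflation and the shift belong to a comparison at a single time point. The hypothesis in Section E is a reduction relative to control, so the natural test is treatment-by-time, from which a constant school difference cancels. Step 5 confirms this, and the point stands. It limits the concern to single-time-point comparisons and to school differences that change over time. Cancellation under a non-identity link, which the plan allows for non-normal outcomes, was not checked.

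Two further points stand. Averaged over what AICc would select, the power gain from a fixed school term is only 0-2 points, even in the single-time-point setting. All the sizes also rest on assumed class numbers, ICC and school differences.

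A reader might infer that the school variance cannot be estimated at all. It can; the estimate simply has no useful precision. A reader might also infer that dropping school biases the trial. Classes are randomised, so the shift in step 4 is conditional on one realised allocation and averages to zero over randomisations. The documents do not say what the realised split is. Nor do they call school a stratum, so randomising classrooms within the schools cannot be read as a promise of balance by school.

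None of this supports the screened two-level random effect. No advantage of it over a fixed term is apparent.

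**Conclusion.** The point holds as a cheap improvement to the specification, not as a threat to validity. With two schools, a 1-df variance decides whether school is modelled, largely by noise and possibly differently for each outcome.

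- **Treatment-by-time:** no effect from a constant school difference in a linear model with complete data. If the difference changes over time, one fifth of the change enters under the assumed 60/40 split.
- **Single time point:** SE about 4-16% larger in the ICC 0.03 scenarios, and a shift of 0.04-0.08 SD under the assumed split with school differences of 0.2-0.4 SD.
- **False positives:** no inflation in any setting checked.

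**What to change.** In the Statistical Analysis Plan:
1. Remove school from the random effects.
2. Add school and school-by-time as fixed effects that are kept for every outcome and are not subject to AICc.
3. Exempt the random effect for the randomised class from AICc removal, because class is the unit of randomisation. This step rests on the design; its size was not worked out here.

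The cost is a sentence or two and 1-3 df (1 for school, 2 for school-by-time over three waves). The SE of the treatment-by-time contrast rises slightly, by about 2% in the imbalanced 20-class example.
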